7.4. Safety Analysis Set

The Safety Set will include all participants administered IP.

8. STATISTICAL ANALYSIS

8.1. General Considerations

All participant data, including those that are derived, that support the tables and figures will be presented in the participant data listings. Some data may be presented only in participant data listings, some may be presented with a corresponding table or figure; these will be indicated in relevant sections below.

For the purpose of all safety and efficacy analyses where applicable, baseline is defined as the last non-missing measurement prior to the first dose of IP. The baseline composite endpoint will be calculated based on baseline individual endpoints.

Unless otherwise specified, continuous endpoints will be summarized with n, mean, standard deviation (SD), median, minimum (min), and maximum (max). The minimum and maximum will be reported with the same number of decimal places as the source (raw) data. Mean and median will be reported to 1 decimal place more than the source (raw) data and standard deviation will be reported to 2 decimal places more than the source (raw) data. Any values that require transformation to standard units (metric or SI) will be converted with the appropriate corresponding precision.

Categorical variables (eg, presence of an adverse event) will be summarized using counts and percentages. Percentages will be presented to 1 decimal place unless otherwise specified.

Participants will be summarized according to randomized treatment for all analyses except for safety analyses. For safety analyses, participants will be summarized according to treatment received.

P-values will be reported to four decimal places, with p-values less than 0.0001 reported as “<0.0001”. P-values larger than 0.9999 will be reported as “>0.9999”.

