^b Complete physical examinations (including MSE and comprehensive neurologic examination) should be performed as specified and additionally as clinically necessary (see Section 12.1.3).

^c Predose on Day 1, supine and standing blood pressure and heart rate will be collected in triplicate at least 15 minutes apart, measured after the participant has been in the supine position for at least 5 minutes and then repeated 1 minute and 3 minutes after standing. Respiratory rate and temperature are collected once predose on Day 1. Vital signs will be collected once predose at all other visits. All postdose vital signs will be collected once at approximately 3 hours (± 60 min) after dosing.

^d ECGs will be collected and read centrally. ECGs will be performed predose and approximately 3 hours (± 60 min) postdose. All ECGs must be performed after the participant has been in a supine position for at least 5 minutes.

 ^f Kinesia ONE will be assessed subsequently to TETRAS Performance subscale part 4 upper limb tremor.

^g The TETRAS Performance and TETRAS ADL subscales will be assessed at Screening and predose at each clinic visit. The TETRAS Performance subscale part 4 upper limb tremor will be assessed before Kinesia ONE. In addition, on Day 15, the TETRAS Performance subscale will be assessed at 5 and 8 hours (± 30 min) postdose. A videographer will record each TETRAS administration.

^h Participants will be trained by study personnel on the use of software applications, Investigational Product Diary, and devices necessary for the conduct of the study.

ⁱ On Day 1, participants will receive the first dose of IP at the research site and will be observed for AEs before leaving the site. A phone call to follow up on any AE(s) will be conducted, if deemed appropriate by the investigator, to review the current status of the participant.

^j Prior medications will be recorded during Screening and will include all medications and supplements taken within the 30 days prior to signing the ICF through the first dose of IP, as well as a complete history of all treatments for ET since the year of diagnosis. Concomitant medications will be recorded thereafter throughout the duration of the study.

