12.1.4. Vital Signs

Vital signs comprise blood pressure and heart rate (supine and standing), respiratory rate, and temperature. Systolic and diastolic blood pressure and heart rate are to be measured after the participant has been supine for at least 5 minutes and then repeated 1 minute and 3 minutes after standing.

Vital signs are measured once at each timepoint with the exception of predose on Day 1, when blood pressure and heart rate are measured supine and standing in triplicate at least 15 minutes apart.

Any abnormality in vital signs will be interpreted by an Investigator as abnormal, NCS; or abnormal, CS in source documents.

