13.3. General Considerations

All participant data, including those that are derived, that support the tables and figures will be presented in the participant data listings. Some data may be presented only in participant data listing, some may be presented with a corresponding table or figure; these will be indicated in relevant sections below. Participants will be summarized according to treatment received.

For the purpose of all primary and secondary analyses where applicable, baseline is defined as the last measurement prior to receipt of IP.

Continuous endpoints will be summarized with number (n), mean, standard deviation, median, minimum, and maximum. In addition, change from baseline values will be calculated at each time point and summarized descriptively. For categorical endpoints, descriptive summaries will include counts and percentages.

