- The suggested order of assessments during clinic visits is: vital signs, TETRAS, Kinesia, ECG, blood sample collection for [REDACTED] clinical laboratory assessments, and questionnaires.
- All assessments will be performed predose unless specified in a footnote.

^a Randomization will occur on Day 1 after meeting all eligibility criteria.

^b Complete physical examinations (including MSE and neurologic examination as parts of physical examination) should be performed as specified and as clinically necessary (see Section 12.1.3 of the protocol).

^c Predose on Day, supine and standing blood pressure and heart rate will be collected in triplicate at least 15 minutes apart, measured after the participant has been in the supine position for at least 5 minutes and then repeated 1 minute and 3 minutes after standing. Respiratory rate and temperature are collected once predose on Day 1. Vital signs will be collected once predose at all other visits. All postdose vital signs will be collected once at approximately 3 hours (\pm 60 min) after dosing.

^d ECGs will be collected and read centrally. ECGs will be performed predose and approximately 3 hours (\pm 60 min) postdose. All ECGs must be performed after the participant has been in a supine position for at least 5 minutes.

^g The TETRAS Performance and TETRAS ADL subscales will be assessed at Screening and predose at each clinic visit. The TETRAS Performance subscale part 4 upper limb tremor will be assessed simultaneous to Kinesia ONE. In addition, on Day 15, the TETRAS Performance subscale will be assessed at 5 and 8 hours (\pm 30 min) postdose. A videographer will record each TETRAS administration.

^h Participants will be trained by study personnel on the use of software applications, Investigational Product diary, and devices necessary for the conduct of the study.

ⁱ Prior medications will be recorded during Screening and will include all medications and supplements taken within the 30 days prior to signing the ICF through the first dose of IP, as well as a complete history of all treatments for ET since the year of diagnosis. Concomitant medications will be recorded thereafter throughout the duration of the study.

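### Read literally, the visible SAP baseline rule uses one of three Day 1 predose blood pressure and heart rate readings; averaging them would be a small gain in precision at almost no cost

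*SAP*

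**What the plan says.** **Collection.** In the protocol (Amendment 4), footnote c to the Schedule of Assessments states that, predose on Day 1, "supine and standing blood pressure and heart rate will be collected in triplicate at least 15 minutes apart". Protocol 12.1.4 agrees: "Vital signs are measured once at each timepoint with the exception of predose on Day 1". Footnote c in SAP Appendix A repeats the scheme, although it prints the day without its number. For the rest of the study it says "Vital signs will be collected once predose at all other visits" and "All postdose vital signs will be collected once at approximately 3 hours" after dosing.

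**Baseline.** SAP 8.1 opens its rule with "For the purpose of all safety and efficacy analyses where applicable" and continues "baseline is defined as the last non-missing measurement prior to the first dose of IP". Protocol 13.3 has the same rule in substance for the primary and secondary analyses: "baseline is defined as the last measurement prior to receipt of IP". The protocol synopsis extends it to efficacy and safety analyses.

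**Use.** Protocol 13.3 has change from baseline calculated and described at each timepoint. SAP Appendix C plans a vital-signs summary table (14.3.4.6.1) and a vital-signs listing (16.2.8.4), and SAP 8.4 rules out hypothesis tests on safety data.

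**The concern.** The protocol asks for three sets of readings at the one timepoint that serves as the reference for every later change. A rule that takes the last reading gives up the precision of the other two.

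The readings include orthostatic measurements. Protocol 5.2 names somnolence as an adverse drug reaction, and 7.4 requires dose action for certain somnolence and dizziness events, so changes in standing blood pressure and heart rate are relevant to this drug's safety profile. A single-reading baseline makes each participant's change noisier than the collected data require.

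There is also a difference of order. The third Day 1 set follows two earlier supine-to-standing cycles, whereas the single set at a later visit follows none.

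**Working it through.** **The plan's own figure.** The documents give no variance, power or precision figure for vital signs. The only stated power is for the primary endpoint (SAP 5.2): a difference of 3 points, SD 3.5, 25 evaluable per group, two-sided 0.05, 85% power. This reproduces: 85.8% by the normal formula, 84.4% by the noncentral t with 48 degrees of freedom, and n = 25 per group. For enrolment, 50/0.85 = 58.8, or 59, against approximately 60 stated. None of this depends on the vital-sign baseline.

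**Does any visible text handle the triplicate?**
- SAP 8.1 adds a baseline provision for composite endpoints but none for replicate readings.
- SAP 8.4 sends multiple values in a visit window to a rule in another section, but the cross-reference is broken.
- The visible window rule, SAP 8.3.2, chooses by distance in days from the target day. Three readings on the same morning are equally distant, so it cannot choose among them.

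The literal result is the third reading, taken at least 2 × 15 = 30 minutes after the first.

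**Precision.** Let w be the variance between replicate readings within a visit, b the visit-to-visit variance within a participant, and k the number of baseline readings averaged. Each later visit has one reading, so

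variance of a change = 2b + w + w/k.

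Scale b + w = 1, so the variance is 2.00 when k = 1. The within-visit share w is an assumption and is varied:

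| Assumed share w | Variance, k = 1 | Variance, k = 3 | Ratio | SD ratio | Fall in SD |
|---|---|---|---|---|---|
| 25% | 2.00 | 1.50 + 0.25 + 0.083 = 1.833 | 0.917 | 0.957 | about 4% |
| 50% | 2.00 | 1.00 + 0.50 + 0.167 = 1.667 | 0.833 | 0.913 | about 9% |
| 75% | 2.00 | 0.50 + 0.75 + 0.25 = 1.50 | 0.750 | 0.866 | about 13% |
| 100% | 2.00 | 0 + 1.00 + 0.333 = 1.333 | 0.667 | 0.816 | about 18% |

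The calculation assumes independent replicate errors and no drift across the three readings.

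**Order effect.** Suppose instead that readings shift by an equal step d from one to the next. The third reading then differs from a first reading by 2d, and the mean of the three differs by (0 + d + 2d)/3 = d. Averaging would halve such a shift but not remove it. The documents give no value for d.

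**The case against.** The strongest objection is redaction. In the SAP contents, the entries between 8.4.1 (Adverse Events) and 8.4.5 (Physical Examination) are blacked out. The body jumps between the same two headings, and Table 4 shows only its adverse-event row. A vital-signs summary is planned, so its analysis text, with any rule for the triplicate, would be expected in that gap. A reader might infer that the SAP definitely throws away two readings. The documents do not support that: what is hidden cannot be called absent, the general rule carries a where-applicable qualifier, and it does not say whether a triplicate counts as one measurement or three. This part of the objection stands, and it makes the point conditional.

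Four narrower objections also stand.
- The documents give no reason for the triplicate. That it was meant to steady the baseline is a reasonable inference but is not stated.
- A reader might see a replication mismatch between baseline and later visits. The literal rule compares one reading with one reading; averaging is what would create three against one. What remains is a possible order effect. No figure supports one, and 12.1.4 already requires at least 5 minutes supine before measurement.
- A reader might take 18% as the expected gain. It is the upper end and needs all within-participant variance to arise within a visit.
- The two unused readings are not lost to the report, because a vital-signs listing is planned.

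Finally, the SAP rule follows the protocol, so changing it is a departure that must be documented. None of this makes a single reading the better baseline when three have been collected.

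**Conclusion.** The point holds as a minor, conditional improvement. On the visible text, the baseline for blood pressure and heart rate is the last of three predose readings, and nothing visible overrides it. Averaging would lower the SD of an individual change by about 4% to 18%, under the stated assumptions on replicate errors, drift and within-visit share. Real differences in response between participants would add to the spread in a summary table, so the proportional gain there would be smaller.

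A reader might infer a biased safety comparison. The documents do not support that. The same rule applies to both arms, so any order or settling effect would enter both, and no bias between arms is claimed. The consequence is less precise descriptive summaries of vital-sign change.

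**What to change.** First check whether the blacked-out text between SAP 8.4.1 and 8.4.5 already defines a triplicate baseline. If it does, no change to the baseline rule is needed.

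If it does not, add to SAP 8.1: *For blood pressure and heart rate, baseline is the mean of the non-missing Day 1 predose triplicate readings, by position and standing time (supine, 1 minute, 3 minutes).* Keep the last-measurement rule for everything else. Record the change in SAP section 6 as a departure from the last-measurement wording in the protocol synopsis and 13.3. Repair the broken cross-reference in SAP 8.4 at the same time.

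The cost is one sentence, one documented departure and a small programming change, made before database lock. No new data are needed, and sample size and power do not change.

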8.2. Background Characteristics

8.2.1. Participant Disposition

The summaries of disposition will include the number of participants who were screened, who were randomized, who received study drug, the number and percentage of participants who completed the study and who prematurely withdrew from the study, primary reasons for not completing the study, who completed treatment, who discontinued treatment prematurely, and primary reasons for discontinuing treatment. Study completion summary and treatment completion summary will be based on participants who received study drug (Safety Set). Percentages will be calculated based on the participants randomized and dosed. These data will be provided by randomized treatment groups. If a participant is rescreened because he/she has been a screen failure the first time, the status of the participant will be determined from the second screening. In the count of screened participants, this participant will be counted only once.

The number of participants in each of the analysis sets will also be summarized and presented by the randomized treatment.

A completer for the study is defined as one who completed the final follow-up visit and is derived from the Study Disposition CRF page with completion question answered Yes. A participant is defined as prematurely discontinuing treatment if treatment ends before the final dose of study drug is taken on Day 28, and is derived from the End of Treatment CRF page with completion question answered No. The main reason is provided in the same CRF page.

Randomization data (date and time of randomization, randomization number, and randomized treatment) and participants excluded from each analysis set will be listed but not summarized.

8.2.2. Protocol Deviations

Protocol deviations will be captured on eCRF and categorized by the study team as major and minor deviations, without any unblinding information. The major deviations will be summarized by type and by actual treatment received using Safety Set. The minor deviations will be included in the listing. The Covid-19 related protocol deviations will also be summarized. The review of major protocol deviations will be completed and the decision on whether the deviation affects efficacy and results in removal of a participant from the Per Protocol Set will be documented before database unblinding.

Inclusion/exclusion violations will be listed but not summarized.

8.2.3. Demographics and Baseline Characteristics

Demographic data (age, sex, race, and ethnicity) and baseline characteristics (height, weight, BMI, dominant hand) will be summarized with descriptive statistics by treatment using the Safety Set.

Baseline subgroups will be summarized for the following categories:

- Race (Black or African American, White, Other)
- Sex (Female, Male)
- Age (<65, 65-80 years)
- BMI (<18.5, 18.5 - <25, 25 - <30, \geq 30 kg/m²)

Listings will be provided for demographics, other baseline characteristics, and informed consent data.

8.2.4. Medical/Surgical History

Medical/surgical history will be coded to Medical Dictionary for Regulatory Activities (MedDRA) terms, using Version 22.1, September 2019, or higher. The MedDRA version will be included in the footnotes of related outputs. Medical/surgical history will be summarized using discrete summary statistics for each MedDRA system organ class (SOC) and preferred term (PT) by treatment group for the Safety Set.

Medical history related to ET (including age at diagnosis, age at onset of ET, whether alcohol helps participant tremor, past treatments for ET, response to therapy, and reason for discontinuation) will be listed. Age at diagnosis, age at onset of ET, past treatment for ET (yes/no), and whether alcohol helps participant tremor will also be summarized. The disease subgroup will be summarized for the following categories:

- Age at essential tremor diagnosis (< 40 years, 40-60 years, >60 years)
- Age participant thinks essential tremor started (< 40 years, 40-60 years, >60 years)
- Years with essential tremor diagnosis (3-<6 years, 6-10 years, >10 years)
- Years since participant thinks essential tremor started (3-<6 years, 6-10 years, >10 years)
- Alcohol helps tremor: Yes (Intermediate, Worked Well), No (No, a little), NA
- Past treatment for essential tremor (Yes/No)

8.2.5. Prior and Concomitant Medications

Medications will be recorded at each study visit and coded into drug class (anatomical therapeutic chemical [ATC] Level 2) and PT using World Health Organization-Drug dictionary (WHO-DD) Global B3 September 2019, or later.

All medications taken within 30 days prior to informed consent through the duration of the study (including start and end dates, route, dose/units, frequency, and indication) will be recorded on the electronic case report form (eCRF); all psychotropic medications taken in the 30 days prior to screening will also be recorded. Those medications taken prior to the initiation of the investigational product will be denoted “Prior”. Those medications taken prior to the initiation of the investigational product and continuing beyond the initiation of the investigational product or those medications started at the same time or after the initiation of the investigational product will be denoted “Concomitant”. Note that medication taken before the initial dosing of investigational product and continued after the initial dosing will be categorized as a prior medication and separately as a concomitant medication.

Medications will be flagged in the listing according to whether they are “Prior” or “Concomitant” as defined above. In the event of a missing start or stop date associated with a medication, only the classification (prior and/or concomitant) will be imputed using the algorithm described in [Appendix B](#). Dates will not be imputed.

Details of prior and concomitant medications will be listed by participant, start date, and verbatim term. Prior and concomitant medications will be summarized separately for the Safety Set as the number and percentage of participants with each medication at both the ATC and PT levels.

8.2.6. Investigational Product Exposure

Total drug exposure (in mg) is defined as the total investigational product in mg for SAGE-324 that was taken during the study. Total drug exposure for participants randomized to placebo is zero unless the participant has taken SAGE-324 by mistake, in which case the

total exposure comes from SAGE-324 exposure. If a participant skips a dose on any of the days, the dose taken is 0 mg.

Total exposure duration to investigational product (in days) is defined as: Date of last dose – date of first dose + 1. Note that this does not exclude days when the dose has been missed.

Percent of the planned exposure received is defined as the total drug exposure, divided by planned exposure, times 100. For participants who complete the treatment period, planned exposure is 28 days of treatment planned, times 60 mg for participants randomized to SAGE-324. For participants who discontinue the treatment early, planned exposure is the total exposure duration times 60 mg for participants randomized to SAGE-324. For participants randomized to placebo, this measure is not applicable.

Total drug exposure, total exposure duration, and percent of the planned exposure received will be summarized using the Safety Set and randomized treatment group. Also, the number and percentage of participants with <80%, 80%-<100%, and 100% of full 60mg dose (4 tablets every day) consumed will be summarized.

8.2.7. Study Drug Adherence

Study drug adherence (%) is defined as the number of tablets taken, divided by the number of tablets planned to be taken, times 100.

The schedule of study drug is 4 tablets of a 15mg strength with a total of 60mg per day, but the investigator may reduce the dose of IP from 60 mg in 15 mg decrements (ie, 60, to 45, to 30 mg). The number of planned tablets intake is defined as follows:

1. If the participant does not have any dose reduction and completes the planned 28 days of treatment, the planned number of tablets is $4*28$

2. If the participant does not have any dose reduction, but discontinues the study drug early, the planned number of tablets is $4*(\text{Date of last dose} - \text{date of first dose} + 1)$

3. If the participant ever has a dose reduction, the planned number of tablets is:

$4*(\text{date of last dose on 60mg or equivalent placebo dose} - \text{date of first dose on 60mg or equivalent placebo dose} + 1)$

$+ 3*(\text{date of last dose on 45mg or equivalent placebo dose} - \text{date of first dose on 45mg or equivalent placebo dose} + 1)$

$+ 2*(\text{date of last dose on 30mg or equivalent placebo dose} - \text{date of first dose on 30mg or equivalent placebo dose} + 1)$.

If the participant does not have dose reduction to 30mg or equivalent placebo dose, the last term is 0.

Study drug adherence will be summarized descriptively using the Full Analysis Set. Number and percentage of participants with study drug adherence in categories <75%, 75-100%, >100% will be provided.

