9. TREATMENT OF PARTICIPANTS

9.1. Description of Investigational Product

SAGE-324 is an orally administered tablet provided in 5 mg or 15 mg (when available) dose strengths. Participants will receive IP (60 mg total dose of SAGE-324 tablets, or appearance-matched placebo tablets) according to the randomization schedule. Additional details regarding IP preparation, formulation, and storage are included in Section 10.

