7.4. Dose Adjustment Criteria

If a participant reports moderate or severe adverse events (as defined in Section 12.2.5) of somnolence, drowsiness, dizziness, or similar events or experiences these events at any severity with associated symptoms such as confusion or balance impairment on Day 1 or at any point during the treatment period, the participant must have a drug holiday (dose interruption) of at least 1 day (missing at least 1 dose) (Table 2). The drug holiday must be followed by reducing the dose of IP from 60 mg to 45 mg (ie, from 4 tablets of 15 mg to 3 tablets of 15 mg).

If the events persist and continue to be moderate or severe, despite the drug holiday and dose reduction, or the participant experiences a new moderate or severe AE of somnolence, drowsiness, dizziness or similar, the participant must have a further drug holiday of at least 1 day and a further dose reduction from 45 mg to 30 mg (from 3 tablets to 2 tablets).

The participant's condition must be closely monitored via phone calls or in-person visits to assess the impact of any drug holiday and dose reduction.

The reduced dose of IP will continue to be administered once daily at the same schedule as specified in the Schedule of Assessments (Table 2). The dose of IP may not be increased for the remainder of the study.

Following a second drug holiday and dose reduction to 30 mg, if the events persist or recur and are moderate or severe, the investigator must discontinue the participant from the IP. The dose may not be reduced below 30 mg.

The investigator will continue to institute drug holidays, dose reductions, or IP discontinuation over and above this minimum as clinically appropriate.

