7.3. Efficacy Analysis Set(s)

[figure not shown]
The Full Analysis Set will include all randomized participants who received any amount of IP and have a baseline and at least one postbaseline efficacy assessment.

The Per Protocol Set will include all participants in the Full Analysis Set without any major protocol deviations that could affect efficacy. The review of major protocol deviations will be completed, and the decision on whether the deviation affects efficacy will be documented before database unblinding. Note that a positive cotinine test on Days 1, 8, 15, 22, or 29 constitutes a major protocol deviation and excludes the participant from the Per Protocol Set. In addition, the Per Protocol Set will exclude full analysis set participants satisfying any of the following conditions:

1. Study Drug Adherence (defined in Section 8.2.7) < 75%
2. Inappropriate drug consumption (typically due to incorrect kit dispensation): if the participant consumed at any time during the study any study drug that the participant is not randomized to

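### For dose-reduced participants, the SAP's adherence formula leaves days off drug between dose levels out of the denominator without limit, so a long gap can still score 100% against the 75% Per Protocol cut

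*SAP*

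**What the plan says.** SAP 8.2.7 defines the measure: "Study drug adherence (%) is defined as the number of tablets taken, divided by the number of tablets planned to be taken, times 100". The dosing basis is "The schedule of study drug is 4 tablets of a 15mg strength with a total of 60mg per day", with 3 tablets at 45 mg and 2 at 30 mg. The planned count then depends on which of three cases applies:

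- Case 1, "If the participant does not have any dose reduction and completes the planned 28 days of treatment": planned tablets are 4 × 28.
- Case 2, "If the participant does not have any dose reduction, but discontinues the study drug early": 4 tablets for every day from first to last dose.
- Case 3, "If the participant ever has a dose reduction, the planned number of tablets is" a sum over dose levels. Each term is that level's tablets per day multiplied by the days from the first to the last dose taken at that level.

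SAP 7.3 removes from the Per Protocol Set any Full Analysis Set participant with "Study Drug Adherence (defined in Section 8.2.7) < 75" per cent.

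Protocol Amendment 4, section 7.4, on which the SAP is based, says that after qualifying sedation-type events "the participant must have a drug holiday (dose interruption) of at least 1 day (missing at least 1 dose"), followed by a step down in dose. A second step down also follows a holiday. No maximum length is given, and the investigator may go beyond the stated minimum.

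**The concern.** In cases 1 and 2 a missed day inside the treatment span stays in the denominator. In case 3 a missed day stays in only if it falls inside a level's own span. Days after the last dose at one level and before the first dose at the next disappear, however many there are. This covers holidays longer than required and also doses simply missed at the changeover.

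The 75% cut can therefore order participants the wrong way round: someone off drug for more than half the treatment period passes, while someone with nearly twice the exposure is removed. SAP 8.3.3.1.4 plans summaries, model estimates and plots in the Per Protocol Set for the primary and secondary endpoints. If that set can hold participants with little exposure, its agreement with the Full Analysis Set says less than it should about the effect in people who took the drug.

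**Working it through.** **Inputs.** Tablets per day of 4, 3 and 2 at 60, 45 and 30 mg, and the three case definitions (SAP 8.2.7); the cut below 75% (SAP 7.3); planned exposure for a SAGE-324 completer of 28 × 60 = 1680 mg (SAP 8.2.6); a holiday of at least 1 day before each reduction (Protocol Amendment 4, section 7.4).

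**The plan's own figure, case 1.** Planned = 4 × 28 = 112.
- 7 days missed: 4 × 21 = 84; 84/112 = 75.0%, kept.
- 8 days missed: 4 × 20 = 80; 80/112 = 71.4%, excluded. Exposure on active drug is 80 × 15 = 1200 mg, and 1200/1680 = 71.4%.

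**Case 3 with a long gap.** 60 mg Days 1–5, off Days 6–20 (15 days), 45 mg Days 21–28 (8 days).
- Planned = 4 × 5 + 3 × 8 = 44. Taken = 44. Adherence = 100%, so the cut is passed.
- Days off: 15/28 = 54%.
- Exposure on active drug: 5 × 60 + 8 × 45 = 660 mg; 660/1680 = 39%.

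**Gap length has no effect.** One day at 60 mg, 26 days off, one day at 45 mg: planned 4 + 3 = 7, taken 7, adherence 100%.

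**Same tablets, same days off, different placement.** Both participants below take 60 mg on Days 1–7 and have 9 days off in total.
- Off Days 8–16, 45 mg Days 17–28: taken 28 + 3 × 12 = 64; planned 64; 100%.
- Off Day 8, 45 mg from Day 9 to Day 28 with 8 days missed inside that span: taken 28 + 3 × 12 = 64; planned 28 + 3 × 20 = 88; 64/88 = 72.7%, excluded.

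**With the correction** (between-level days beyond one per reduction counted at the next level's rate):
- Long-gap example: 44/(44 + 14 × 3) = 44/86 = 51%, excluded.
- The 9-day pair: the first becomes 64/(64 + 8 × 3) = 64/88 = 72.7%, equal to the second.
- Two 1-day holidays (7 days at 60 mg, 7 at 45 mg, 12 at 30 mg): 73/73 = 100%, so the required minimum costs nothing.

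**The case against.** The best defence is that adherence is not exposure. On a required holiday no tablets are planned, so leaving that day out is right, and the reduced participant may be following instructions while the never-reduced one is not. This stands for the required day. It does not justify leaving out days without limit, or leaving out doses merely missed at a changeover.

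SAP 8.2.6 does measure exposure against 28 × 60 mg and would show the example at 39%. However, it does not feed the Per Protocol Set and is not applicable to placebo.

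The blinded review of major deviations (SAP 7.3 and 8.2.2) could remove a participant with a long gap. It is discretionary, and a long holiday is not by itself a deviation when the protocol sets only a minimum. So it would go too far to infer that such a participant is certain to remain in the Per Protocol Set.

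The 15-day gap is a constructed case. It spans two clinic visits, and the protocol asks for close monitoring around holidays. The documents do not say how often long gaps occur.

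Two stronger readings are not supported. A reader might infer a demonstrated imbalance between arms. Reductions follow somnolence-type events, and the protocol names somnolence as an adverse drug reaction, so more of the leniency could fall on active drug; but no rates by arm are given. A reader might also infer from superseded amendments ("SAGE-324 is an orally administered tablet provided in 5 mg or 15 mg (when available) dose strengths") that the tablet count fails for 5 mg supply. Amendment 4 lists 15 mg tablets only, the SAP rests on Amendment 4, and nothing shows that 5 mg tablets were dispensed.

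**Conclusion.** The gap in case 3 is real and reproduces exactly. A dose-reduced completer can be off drug for more than half of the 28 days, score 100% and pass the cut, while a never-reduced completer missing 8 days fails it. The 100% score requires the off-drug days to lie between levels. The comparison is between participants who complete treatment: a never-reduced participant who stops at Day 20 scores 80/80 = 100% under case 2.

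The consequence is limited to the adherence summary and the supportive Per Protocol analyses. A reader might infer that the primary result is at risk; it is not, because that analysis uses the Full Analysis Set. The number of participants affected, and the effect on any Per Protocol estimate, cannot be judged from the documents. The point is worth correcting because a written rule gives a perverse result and the repair is small.

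**What to change.** Keep the tablet-based criterion. In SAP 8.2.7 case 3, add to the planned count all days between the last dose at one level and the first dose at the next, less the one required holiday day per reduction, at the tablet rate of the level at which dosing resumes. Apply this identically to active and placebo, and fix it before unblinding.

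An alternative is to keep the 75% tablet rule and add a second condition excluding completers dosed on fewer than 75% of days from first dose to Day 28. The two agree on the long-gap example (13/28 = 46% of days) but can differ near the cut. For 60 mg Days 1–7, off Days 8–15, 45 mg Days 16–28, the tablet version gives 67/(67 + 7 × 3) = 76.1% and the day version 20/28 = 71.4%. One should be chosen in advance. Days dosed should not replace the tablet rule: someone taking 1 of 4 tablets daily scores 28/112 = 25% now and is excluded, but would count as dosed on 28 of 28 days.

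The cost is a few lines of SAP text, using dose dates that 8.2.7 already needs. The drawback is that some participants with long investigator-directed holidays leave the Per Protocol Set. That is selection on tolerability after randomisation, so their number should be reported by arm. No dosing or holiday rule changes.
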